Visit Identifier Abbreviations used in this table may be found in Appendix 17	Screening	Treatment Period									EOT	4-week Follow- up	90-day Follow- up for irAEs	Notes
		Cycle 1 =28 days				Cycle ≥ 2 (28 days)								
Study Day	-28 to -1	1	2 ^a	8	15	16 ^a	22	1	8 ^b	15				
 Additional visit window may be allowed after discussion and agreement between investigator and sponsor. 
a: End of inpatient observation (PK, ECG, vital signs).
 
b: This D8 visit is only applicable for Cycles 2 and 3, whereas, C3D8 is applicable for PK/PD and ECG only.

Visit Window (days)		± 2		± 2	± 2			± 2	± 2	± 2		± 7	± 7	
Study Intervention														
PF-07260437		X (priming dose)		(X ^c)	X			X		X				
 C1D1 is priming dose and C1D15 is full/maintenance dose. c: A 2-step priming may be considered on C1D1 and C1D8. See Section 4.1 for additional information.

Table 3. Study Schedule of Assessments – Part 1 With Priming

Visit Identifier Abbreviations used in this table may be found in Appendix 17	Screening	Treatment Period									EOT	4-week Follow- up	90-day Follow- up for irAEs	Notes
		Cycle 1 =28 days												
Study Day	-28 to -1	1	2 ^a	8	15	16 ^a	22	1	8 ^b	15				
 Additional visit window may be allowed after discussion and agreement between investigator and sponsor.
Visit Window (days)		±2	±2	±2		±2	±2	±2	±2	±2		±7	±7	
a: End of inpatient observation (PK, ECG, vital signs).
 
b: This D8 visit is only applicable for Cycles 2 and 3, whereas, C3D8 is applicable for PK/PD and ECG only.

Premedication		(X)	(X ^d)	(X)			(X)		(X)					
 Prophylactic premedication is not allowed during the DLT evaluation period during initial dose escalation. However, if the participant experiences an infusion related reaction (IV), allergic reaction, significant injection site reaction, CRS, fever/chills, allergic reaction, nausea/vomiting, hypotension, or pain, appropriate treatment should initiate and premedication as prophylaxis may be considered for subsequent injections as well as for new participants. See Section 6.1.1.1 for additional information. d: Only applicable to 2-step priming

Table 3. Study Schedule of Assessments – Part 1 With Priming

Visit Identifier Abbreviations used in this table may be found in Appendix 17	Screening	Treatment Period									EOT	4-week Follow- up	90-day Follow- up for irAEs	Notes

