- **Priming Dose:** A priming dose approach in the next dose level may be initiated if a dose level induces \geq Grade 2 CRS (lasting for >24 hours) occurs in >1 participant despite treatment with tocilizumab and/or vasopressors. Initially, a single priming dose may be administered on C1D1 at 1 dose level below the dose level in which the recurrent \geq Grade 2 CRS event was observed. The first full dose will be administered on C1D15 with a starting full dose that is not higher than the full dose at which the recurrent \geq Grade 2 CRS event occurred. Depending on the observed safety and tolerability profile, dose escalation of the full dose may proceed with full dose increased by a maximum of 200%. If \geq Grade 2 CRS is observed after the administration of full doses, a 2 (or more) step-up priming dose approach may also be implemented (for example, 2 priming doses administered on C1D1 and C1D8, respectively); the initial priming dose will be at a dose level where predicted probability of \geq Grade 2 CRS is $<20\%$. In addition, dose finding without priming may still continue in parallel if MTD without priming has not been reached and RDE without priming has not been determined. Finally, additional priming dose strategies (eg, additional doses, different dosing levels and intervals) may be investigated based on emerging data.

All Part 1 participants in cohorts without a priming dose will be observed inpatient for at least 48 hours after the first SC dose (or the first IV dose, as applicable) on C1D1 and for at least 8 hours after the second SC dose (or the second IV dose, as applicable) on C1D15. Participants in cohorts with a priming dose will be observed inpatient for at least 24 hours after the first SC priming dose (or the first IV priming dose administration, as applicable) on C1D1 and 24 hours after the second (full) dose on C1D15 ([Table 7](#)). Modification of inpatient observation period might be allowed based on emerging safety data and will require discussion and agreement between investigator and sponsor.

- Participants who experience Grade ≥ 3 infusion-related adverse events (IV administration) or clinically significant cytokine release syndrome must be hospitalized for at least 24 hours for at least 4 doses subsequently (two cycles). If subsequent doses are tolerated without recurrence of Grade ≥ 3 infusion-related adverse events or clinically significant cytokine release syndrome, outpatient PF-

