4.3.2. Justification for Priming Dose Regimen

Priming dose approaches are commonly applied for T-cell engager bispecific modalities to initially sensitize the immune system at lower doses to reduce rate and grade of CRS ([Costa et al, 2019](#); [Garfall, 2020](#); [Madduri et al, 2020](#); [BLINCYTO \(blinatumomab\), 2021](#)). A priming dose approach may be initiated if a dose level induces \geq Grade 2 CRS (lasting for >24 hours) occurs in >1 participant despite treatment with tocilizumab and/or vasopressors. Initially, a single priming dose will be administered on C1D1 at 1 dose level below the dose level whereby the \geq Grade 2 CRS event was observed. The first full dose will be administered on C1D15 with a starting full dose that is 100% higher than the priming dose. Depending on the observed safety and tolerability profile, dose escalation on the full dose may still proceed with up to 3-fold increment from current full dose level. If \geq Grade 2 CRS is observed after the administration of full doses, a 2 step-up priming doses approach may also be implemented with the 2 priming doses administered on C1D1 and C1D8, respectively; both priming doses will be at dose levels where predicted probability of \geq Grade 2 CRS is $<20\%$.

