### 5.2 General Methods

The data are summarized by dose level cohort, defined by the initial dose of the study intervention administered to participants. DLT rates at the study dose levels will be presented via mean and medians and a Bayesian credible interval based on the posterior density from the full probability model. This information will also be used for the dose escalation decision meetings. Unless otherwise specified, all other summaries will be presented by dose level cohort and overall. Additionally, summary tables will include the total sample size and number missing/not reported. Lastly, missing data may be imputed according to section 0 and unless otherwise specified missing values that are not imputed will be excluded from the analysis.

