#### 6.1.3 Laboratory abnormalities (Part 1 and Part 2)

- Analysis methodology:

Laboratory abnormalities will be presented as tables and characterized by type, frequency, severity (as graded by NCI CTCAE version 5.0), and timing. For laboratory tests without CTCAE grade definitions, results will be categorized as normal, abnormal high/low, or not done. The number and percentage of participants who experienced laboratory test abnormalities will be summarized according to worst toxicity grade observed for each laboratory assay. Shift tables of baseline grade to worst post-baseline grade will be provided. Quantitative summaries for change from baseline and percent change from baseline for the laboratory tests may be provided, if deemed necessary. These summaries will be

presented for the entire on-treatment period and for the various subgroups of the study (by dose level for Part 1 and by expansion cohort for Part 2).

Hematology, serology and coagulation lab results can be combined into one summary output. Separate summaries will be created for chemistry tests. Urinalysis and pregnancy tests will not be summarized and will only be listed.

- Missing data: Missing lab values will not be imputed.

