### 6.5.3 Study Treatment Exposure

The Safety Analysis Set will be used.

Dose modifications are described in the protocol. The following will be summarized by treatment dose level and overall:

- Number of subjects;
- Median and range of number of treatment cycles started;
- Number (%) of subjects starting a treatment cycle (1, 2, 3...);
- Number (%) of dose interruptions (include both known and unknown dates). Dose interruptions is defined as as a planned dosing day with 0 mg total dose administered. Missing doses on unknown dates will be included in the summary. Note: Dose interruptions apply to unexpected dose interruptions and not the one-week treatment holiday given in each treatment cycle;
- Number (%) of dose interruptions related to AEs, defined as “Was the Actual Dose adjusted from planned?” = “ADVERSE EVENT(S)” and “Latest Action Taken with Study Treatment:” = “DOSE INTERRUPTED”;
- Number (%) of subjects with dose reductions. A dose reduction is defined as a day when the actual dose is less than the planned dose at enrollment and the acutal dose is greater than 0 mg (i.e., missed doses are not counted as a reduction);
- Number (%) of dose reductions related to AEs, defined as “Was the Actual Dose adjusted from planned?” = “ADVERSE EVENT(S)” and “Latest Action Taken with Study Treatment:” = “DOSE REDUCED”;
- Number (%) of participants with dose reductions or interruptions for each reason (AE vs insufficient clinical response vs Other);
- Days on treatment (median, range).
- Number of treatment cycles received per subject (median, range);
- Number of treatment cycles received before 1st reduction (median, range);
- Number of treatment cycles received before 1st interruption (median, range).

The following will be summarized for cumulative dose by dose level:

- Summary statistics (mean, median, standard deviation and range) of cumulative dose and cumulative percent of administered dose (compared to planned dose);
- Actual dose intensity (mg/day): Defined as cumulative actual dose received (mg) divided by the number of doses scheduled per protocol during treatment period;
- Ratio of actual dose intensity to planned dose intensity. Where planned dose intensity is defined as a participant's planned starting dose.

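### If priming is used, SAP 5.2 files Part 1 participants under their priming dose, and the single reference dose in SAP 6.5.3 misstates dose intensity and reductions whichever dose is meant

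*SAP*

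**What the plan says.** SAP 5.2 sets the grouping rule: "The data are summarized by dose level cohort, defined by the initial dose of the study intervention administered to participants". It is the default for every summary not otherwise specified. SAP 6.1.3 presents laboratory abnormalities "by dose level for Part 1 and by expansion cohort for Part 2", and SAP 6.3 presents Part 1 response by dose level. Neither defines dose level again for primed participants.

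In the priming schedule (Protocol 1.3.2, Table 3), "C1D1 is priming dose and C1D15 is full/maintenance dose". Protocol 4.1 places the priming dose one level below the level at which CRS recurred and then escalates the full dose: "dose escalation of the full dose may proceed with full dose increased by a maximum of 200" percent. It also allows dose finding without priming to continue in parallel. On the first full dose, Protocol 4.1 gives only a ceiling (the full dose at which CRS recurred), whereas Protocol 4.3.2 gives a value: "The first full dose will be administered on C1D15 with a starting full dose that is 100% higher than the priming dose".

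SAP 6.5.3 uses a single reference dose for exposure. For reductions: "A dose reduction is defined as a day when the actual dose is less than the planned dose at enrollment" (and above zero). For intensity, "planned dose intensity is defined as a participant's planned starting dose". Actual dose intensity carries the unit mg/day, but the cumulative dose is "divided by the number of doses scheduled per protocol during treatment period".

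**The concern.** A primed participant has at least two planned dose levels, and these rules allow for one. The dose that defines the regimen, and that is escalated, is the full dose. The label follows the first dose administered, which is the priming dose.

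Two things follow if the text is applied as written. Primed and unprimed participants can share a Part 1 column, and several full-dose levels can sit under one priming-dose label. Adverse events, laboratory abnormalities and responses at a higher full dose would then be reported under a lower dose. Separately, the intensity ratio and the general reduction count in SAP 6.5.3 cannot be right for a participant dosed exactly as planned.

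SAP 3.1 says safety, laboratory, PK and other data are used with the BLRM recommendation at each escalation and for MTD/RDE determination. Mislabelled by-dose tables would weaken that descriptive evidence.

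**Working it through.** The documents give no figure to reproduce here, so the SAP definitions are applied directly to worked examples.

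**Inputs.** Dose ladder 100, 300, 900 µg (Protocol Table 8); about 3 participants per dose level (Protocol 4.1). Assumptions: CRS trigger at 900 µg, so priming at 300 µg; first full dose shown as both 600 µg (twice the priming dose, Protocol 4.3.2) and 900 µg (the ceiling in Protocol 4.1).

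**Cohort label.** The initial dose administered is 300 µg for the unprimed 300 µg cohort, for 300/600 and for 300/900.
- One primed cohort run: 3 unprimed + 3 primed = 6 participants under the 300 µg label, half of them on a higher full dose.
- Both primed cohorts run: 3 + 3 + 3 = 9 participants under one label, on full doses of 300, 600 and 900 µg.

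**Intensity ratio.** With one priming dose P, full dose F and k doses as planned, actual intensity is [P + F(k − 1)]/k. Divide by the reference dose. A reduction is a dosing day with 0 < actual dose < reference. For k = 4:

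| Doses given (µg) | Mean per dose | Reference = priming dose | Reference = full dose | Reference = dose planned for each day |
|---|---|---|---|---|
| 300, 600, 600, 600 (as planned) | 2100/4 = 525 | 525/300 = 175%, 0 reductions | 525/600 = 87.5%, 1 reduction | 525/525 = 100%, 0 reductions |
| 300, 900, 900, 900 (as planned) | 3000/4 = 750 | 750/300 = 250%, 0 reductions | 750/900 = 83.3%, 1 reduction | 750/750 = 100%, 0 reductions |
| 300, 600, 300, 300 (cut from dose 3) | 1500/4 = 375 | 375/300 = 125%, 0 reductions | 375/600 = 62.5%, 3 reductions | 375/525 = 71.4%, 2 reductions |
| 300, 900, 300, 300 (cut from dose 3) | 1800/4 = 450 | 450/300 = 150%, 0 reductions | 450/900 = 50.0%, 3 reductions | 450/750 = 60.0%, 2 reductions |

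**Does this depend on the doses chosen?** No. For any F > P and k ≥ 2, the ratio as planned is 1 + (k − 1)(F/P − 1)/k, above 1, against the priming dose. Against the full dose it is 1 − (1 − P/F)/k, below 1. Over 52 doses (two years at Q2W) with 300/600, the values are 198.1% and 99.0%. The full-dose distortion therefore fades with time on treatment, while the priming-dose distortion grows towards F/P. An unprimed participant dosed as planned scores 100% with no reductions, so the problem is specific to priming.

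**Unit.** Dividing by scheduled doses gives an amount per dose. At Q2W, 525 µg per dose is 525/14 = 37.5 µg per day, so the mg/day label is out by a factor of 14. This applies with or without priming.

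**The case against.** The strongest reply is that the initial-dose clause has an ordinary purpose: it keeps participants in their entry cohort after a dose reduction or an intra-participant escalation. Both documents speak of cohorts with and without priming, and the sponsor assigns each Part 1 participant's dose level in writing before dosing (Protocol 6.3.1). The intent may well have been the assigned level. But SAP 5.2 says administered, and the response listing in SAP 6.2.4 also carries the Day 1 dose actually received. Even if the assigned level was meant, the SAP 6.5.3 problem remains.

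Several safeguards are real:
- The BLRM posterior is evaluated separately with and without priming.
- SAP 3.5.1 replaces Cycle 1 with the 42-day period in AE summaries for primed participants. This changes the reporting window, not the cohort label.
- Part 2 efficacy and laboratory summaries are by expansion cohort.
- The AE-related reduction count comes from CRF fields, and the by-cycle listings show planned against actual dose.
- The SAP 6.5.3 summary of cumulative percent of administered dose would be correct if planned dose is taken visit by visit.

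These limit the harm but do not correct the label, the intensity ratio or the general reduction count.

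It can also be said that a scheduled priming dose is not a toxicity-driven reduction in the sense of Protocol 6.5.3. That is so, but the SAP defines a reduction arithmetically and gives no exemption for priming. In the worked example, 600 µg meets both protocol sections, so the 900 µg rows apply only under Protocol 4.1 alone or after later escalation. Finally, priming is optional, and reviewers in an open-label trial would know who was primed. That bears on severity, not on whether the rule is right.

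**Conclusion.** The concern holds. If priming is used, SAP 5.2 as written puts Part 1 participants under their priming dose in the descriptive AE, laboratory, exposure and response tables. SAP 6.5.3 gives no reading under which a compliant primed participant scores 100% with no reduction. In the illustration the ratio is 175% or 250% on one reading and 87.5% or 83.3% on the other, with all primed participants counted as reduced on the second. On the first, a cut to the priming dose goes uncounted.

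The sizes rest on the assumed doses, four doses per participant and 3 participants per cohort; the direction needs only a priming dose below the full dose. The labelling half relies on the literal reading of administered; the exposure half does not. Nothing here touches the DLT model. The point should be corrected before any primed cohort is tabulated. Apart from the unit error, it has no effect if priming is never used.

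**What to change.** - **SAP 5.2:** define the Part 1 dose level cohort by assigned regimen: full dose, priming schedule (none, or the priming dose or doses and steps) and route. Route is needed because SC level −1 and the example IV starting dose are both 60 µg.
- **SAP 6.5.3, reductions:** count a reduction when the actual dose is above zero and below the dose planned for that dosing day.
- **SAP 6.5.3, intensity:** define planned intensity as the sum of planned doses, priming included, divided by the number of scheduled doses. State both intensities per dose instead of mg/day.
- **Protocol 4.1 and 4.3.2:** reconcile the two statements on the first full dose after priming, because the planned doses used above depend on them.

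The SAP changes cost wording and table-shell labels only, with no new data collection and no change to the BLRM.

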### **5.2.1 Analyses for Binary Endpoints**

Binary data will be summarized using number of unique patient incidence, and confidence interval for binomial proportions will be presented if warranted using Clopper-Pearson exact method.

Binary endpoints in this study include complete response (CR), partial response (PR), stable disease (SD), progressive disease (PD), disease control rate (DCR), objective response rate (ORR) based on RECIST v1.1, and irCR, irPR, irSD, irPD and irDCR based on irRECIST. Descriptive statistics along with the corresponding 2-sided 95% confidence intervals (CI) using Clopper-Pearson exact method will be provided for these endpoints if the sample size per cohort permits.

### **5.2.2 Analyses for Continuous Endpoints**

Continuous data will be summarized with the mean, median, minimum, maximum, coefficient of variation, standard deviation, and 2-sided 95% confidence intervals if the sample size permits.

### **5.2.3 Analyses for Categorical Endpoints**

Categorical data will be summarized by number of unique patient incidence.

### **5.2.4 Analyses for Time-to-Event Endpoints**

The time-to-event data will be presented for individual patient, by dose level cohort, and overall when applicable. Time-to-event endpoints will be summarized using the Kaplan-Meier method and estimated survival curves will be displayed graphically when appropriate. Graphs will describe the number of participants at risk over time. The median, quartiles, and probabilities of an event at particular points in time will be estimated by the Kaplan-Meier method, when possible based on the number of observed events. Confidence intervals for medians and quartiles are based on the Brookmeyer-Crowley method. Confidence intervals for the estimated probability of an event at a particular time point will be generated using the Greenwood formula.

## **5.3 Methods to Manage Missing Data**

For the analysis of safety endpoints, the sponsor data standard rules for imputation will be applied. See Clinical Data Interchange Standards Consortium (CDISC) and Pfizer data standard (PDS) Safety Rulebooks for details.

### **5.3.1 Missing Dates**

In compliance with Pfizer standards, if the day of the month is missing for any date used in a calculation, the 1st of the month will be used to replace the missing date unless the calculation results in a negative time duration (eg, date of onset cannot be prior to day one date). In this case, the date resulting in 0 time duration will be used. Pfizer standards are also used if both month and day are missing (Jan 1 unless negative time duration). This excludes the pharmacokinetic and ECG analyses, which will only use the actual date collected or if date not available deem the data missing.

### 5.3.2 Efficacy Analysis

No imputation will be performed for tumor assessments that will be used for the binary efficacy endpoints. Every effort will be made to retrieve data in the CRF, however missing data will be left as is. The reasons for missing tumor assessments will be collected.

For the time-to-event endpoints, the missing data handling method will be censoring.

### 5.3.3 Pharmacokinetics

#### 5.3.3.1 Concentrations Below the Limit of Quantification

In all data presentations (except listings), concentrations below the limit of quantification (BLQ) will be set to zero. (In listings BLQ values will be reported as “<LLQ”, where LLQ will be replaced with the value for the lower limit of quantification.)

#### 5.3.3.2 Deviations, Missing Concentrations and Anomalous Values

In summary tables and plots of median profiles, statistics will be calculated having set concentrations to missing if 1 of the following cases is true:

1. A concentration has been collected as ND (i.e., not done) or NS (i.e., no sample),
2. A deviation in sampling time is of sufficient concern or a concentration has been flagged anomalous by the pharmacokineticist.

Note that summary statistics will not be presented at a particular time point if more than 50% of the data are missing.

An anomalous concentration value is one that, after verification of bioanalytical validity, is grossly inconsistent with other concentration data from the same individual or from other participants. For example, a BLQ concentration that is between quantifiable values from the same dose is considered as anomalous. Anomalous concentration values may be excluded from PK analysis at the discretion of the PK analyst.

### 5.3.4 Pharmacokinetic Parameters

Actual PK sampling times will be used in the derivation of PK parameters.

If a PK parameter cannot be derived from a subject's concentration data, the parameter will be coded as NC (i.e., not calculated). (Note that NC values will not be generated beyond the day that a subject discontinues.)

In summary tables, statistics will be calculated by setting NC values to missing; and statistics will be presented for a particular dose with  $\geq 3$  evaluable measurements.

If an individual subject has a known biased estimate of a PK parameter (due for example to dosing error), this will be footnoted in summary tables and will not be included in the calculation of summary statistics or statistical analyses.

